#### **10.4.1 Reporting Adverse Events**

The sponsor-investigator assumes responsibility for IND safety reporting to the FDA and participating investigators, in accordance with regulations under 21 CFR 312.32. The sponsor-investigator will be responsible for all communications with the FDA under the investigator's IND. Any correspondence to any government health authority regarding safety issues will be simultaneously copied to the drug-sponsor (Vir/GSK). The drug-sponsor will cross-report the relevant events to the VIR-7831 parent IND in accordance with 21 CFR 312(c).

For determination of IND safety reporting, AE attribution will be assessed according to the suspected adverse reaction definition described in 21 CFR 312.32 as an AE for which there is a reasonable possibility that the drug caused the adverse event where "reasonable possibility" means there is evidence to suggest a causal relationship between the drug and the AE. Suspected adverse reactions that are serious, related, and unexpected will be reported to the FDA as an IND safety report, in accordance with regulations under 21 CFR 312.32.

SAEs as defined in Section 10.1 will be recorded on the appropriate SAE report form.

#### **Reporting to FDA**

- SAEs related to the study drug that are unexpected, and fatal or life-threatening will be reported to the FDA no later than 7 calendar days after SAE awareness.
- SAEs related to the study drug that are unexpected and serious (not fatal or life-threatening) are to be reported to the FDA no later than 15 calendar days after SAE awareness.
- All other SAEs will be submitted with the FDA Annual Report in summary form.

#### **Reporting to GSK and Vir**

- Any SAE, regardless of the causal relationship to Study Drug, occurring after the Subject has signed the Informed Consent Form through study end should be reported to the drug-sponsor (Vir/GSK) (safety mailbox provided below), no more than 24 hours after SAE awareness.
- All other events of special interest, including reports of pregnancy, abuse, misuse, medication error, overdose, and occupational exposure are to be captured using the SAE procedures but are to be considered as SAEs only if they meet serious criteria. All events of these types should be reported to Vir and GSK, regardless of whether or not there is an associated AE or SAE, no more than 24 hours after awareness.
  - If a pregnancy is reported during the study period, pregnancy information will be recorded and submitted to Vir/GSK within 24 hours of learning of the female participant pregnancy. While pregnancy itself is not considered to be an AE or SAE, any pregnancy complication or elective termination of a pregnancy for medical reasons will be reported as an AE or SAE.
  - The participant will be followed to determine the outcome of the pregnancy and for up to 1 year after birth. The investigator will collect follow-up information on the participant and the neonate/child and the information will be forwarded to Vir/GSK.
- Follow-up information to all initial reports will be sent to Vir and GSK no more than 24 hours after awareness.
- SAE reports and pregnancies shall be sent to GSK CMG via email at [[contact]](mailto:[contact]) or alternatively faxed to [[name]]([contact]) if email is unavailable.

- Adverse Events of grade 2 or higher severity and Unexpected Adverse Events that are not attributable to the underlying disease for which HCT was performed, or not attributable to graft-versus-host disease (GVHD), not attributable to complications of immunosuppressive medications, and which is different from what is expected in the clinical course of a HCT recipient will also be reported to Vir Biotechnology at least annually.

**Reporting to IRB:** The investigator or designee must report events to the FHCRC IRB in accordance with the policies of the IRB.

- All problems, events (whether occurring on-site or off-site), or information which in the opinion of the investigator are unexpected, related, or possibly related to the research, and serious or suggest that the research places research participants or others at a greater risk of physical or psychological harm than was previously known or recognized must be reported to the IRB not later than ten (10) calendar days after he or she first becomes aware of it.
- All serious or continuing noncompliance with federal laws relating to research involving human subjects, or with the requirements or determinations of the IRB will be reported within ten (10) calendar days of discovery of the event.

## 11. STUDY WITHDRAWAL/DISCONTINUATION

Patients can withdraw from the study at any time point. Patients are also able to withdraw from study activities but still have safety outcomes recorded from review of the electronic medical record for safety purposes and to record safety outcomes. If conditioning is unexpectedly delayed by > 14 days after administration of VIR-7831, the subject can stay in the study but will not count towards the target sample size and will be excluded from the primary analysis. This would allow continued safety monitoring and analysis of secondary and exploratory objectives. Patients may also be discontinued from participating in the study at the Investigator's discretion.

## 12. STATISTICAL CONSIDERATIONS

### 12.1 Type of Study

This is a phase 1, prospective, open-label study to assess pharmacokinetics post-transplant of an extended half-life mAb targeting SARS-CoV-2.

#### 12.1.1 Pharmacokinetics Assessment

- Primary objective: To determine the levels of VIR-7831 mAb post-transplant in serum over time. Both compartmental and non-compartmental analyses are used to assess pharmacokinetic parameters. The half-life of the anti-SARS-CoV-2 monoclonal antibody and neutralizing antibody titers in the serum will be calculated by a one-phase exponential decay model. We will compare fold-changes in antibody levels by normalizing to pre-transplant levels for each subject. Levels of VIR-7831 can be measured using an idiotypic antibody assay that is not affected by COVID-19 infection or vaccination. In addition, to half-life, we will calculate  $C_{max}$ ,  $T_{max}$ , AUC from the concentration over time plots.

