## 2. STUDY PURPOSE AND RATIONALE

HCT recipients are most vulnerable to infection during the early post-transplant period; however, active immunization against SARS-CoV-2 is thought to be ineffective during this period because all patients continue on immunosuppressive medications to prevent graft-versus-host disease (GVHD) and the immune system is not yet fully reconstituted(18, 19). In addition, most HCT recipients lose their immunity to various pathogens as soon as during the first months after transplant, irrespective of pre-transplant donor or recipient vaccinations. Current guidelines recommend considering vaccination at least three months

after transplant even though efficacy is unknown and may be sub-optimal. Passive immunization with monoclonal antibodies (mAbs) against SARS-CoV-2 administered pre-transplant represents a strategy to reduce the risk of COVID-19 among HCT recipients this the period of vulnerability when vaccination is not recommended or when vaccine responses may be sub-optimal.

This is a prospective, open-label phase 1 clinical trial that will enroll hematopoietic stem cell transplant candidates to receive the mAb VIR-7831 targeting SARS-CoV-2. The primary objective is to assess the pharmacokinetics of this extended half-life mAb post-transplant.

Previous studies have found that the half-life of CMV- and RSV-specific antibodies is 7-10 days in HCT recipients which is significantly less than the 21-day half-life of IgG in healthy adults(20-22). Although the mechanism of this accelerated decay is unclear, one possible explanation is increased antibody loss through graft versus host disease (GVHD)-related gut leakage which may be more common among recipients of mis-matched unrelated donor stem cell transplants. Monoclonal antibodies against SARS-CoV-2 administered pre-transplant represent a strategy to reduce the risk of COVID-19 among HCT recipients. This study will assess the pharmacokinetics of one such monoclonal antibody with regards to half- in the serum in both autologous and allogeneic transplant recipients. As an exploratory analysis, nasal antibodies may also be measured to determine the bioavailability of VIR-7831 in the nose since this is the portal of entry for infection by SARS-CoV-2.

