#### Nature of Illness and Treatment Criteria

- 3) Patients must be undergoing HCT (any donor or stem cell source including autologous or cord blood)
- 4) History of prior transplants are permitted
- 5) History of COVID-19, history of vaccination for SARS-CoV-2, positive PCR of a respiratory specimen for SARS-CoV-2 as long as it is not within four weeks from conditioning, or seropositivity for SARS-CoV-2 are permitted
- 6) History of SARS-CoV-2 infection or vaccination of the donor are permitted.
- 7) Post-enrollment vaccination is anticipated and permitted
- 8) Administration of IVIG before or during the study is permitted

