## 9.2 Infusion Response Assessment

**Bioanalytical PK method:** This assay will be performed by Vir Biotechnology. A validated Electrochemiluminescence (ECL) Immunoassay is used to quantify sotrovimab in human serum samples. AbD34205 mu IgG2a (an anti-LS monoclonal antibody against the Fc region of VIR-7831) is coated onto an MSD High Bind plate (ECL capable). Sotrovimab in standards, QC's, controls and samples is captured onto the coated plate. After thorough washing of the wells to remove the unbound drug, Ruthenylated AbD42688 rFab is added to the wells. The conjugate binds to the captured sotrovimab. Following the incubation of the detection reagent, the plate is washed followed by addition of freshly prepared 1% formaldehyde for fixation and MSD read buffer. The assay plate is then read using an MSD ECL plate reader. Anti-drug antibodies may also be analyzed.

**Neutralization assay:** This assay may be performed at the Fred Hutch as an exploratory analysis using a SARS-CoV-2 pseudotyped virus assay as previously described(29). Briefly, this is a functional test to assess the ability of antibodies to bind and prevent infection of cultured cells with a pseudotyped virus that utilizes the spike protein of SARS-CoV-2 for infection and expressed luciferase. The endpoint neutralization titer of the serum will be determined as the dilution resulting in 50% neutralization ( $ID_{50}$ ).

**Binding antibodies (IgG):** This assay will be conducted at the Fred Hutch. We will use an indirect enzyme-linked immunosorbent assay (ELISA) or Luminex assay for quantification of anti-SARS-CoV-2 spike and nucleoprotein IgG and total IgG as previously described(30). Briefly, 96-well microtiter plates will be coated with recombinant SARS-CoV-2 spike or nucleoprotein or polyclonal goat anti-human IgG. Serum samples will be initially diluted at 1:100 and nasal samples will be diluted 1:10. Diluted specimens will be incubated in duplicate on the plate followed by addition of secondary goat anti-human IgG-horseradish peroxidase (HRP). Optical densities (OD) will be measured with a spectrophotometer. Plates will include a positive control monoclonal antibody against SARS-CoV-2 spike. If available, donor serum may also be analyzed using an ELISA assay for SARS-CoV-2 spike and nucleocapsid protein to ascertain SARS-CoV-2 infection and vaccination status.

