## 12.2 Secondary Objectives

- Secondary and exploratory objectives: We will compare antibody levels in autologous vs. allogeneic transplant, cord vs. non-cord allogeneic transplant, matched vs. mismatched transplants, in patients with and without GVHD, and in patients with and without diarrhea to test if HLA-mismatching, GVHD, and/or diarrhea are associated with accelerated antibody decay. Diarrhea will be assessed on the weekly questionnaire and the presence/severity/tissue involvement of GVHD will be assessed by review of the medical record at all timepoints indicated in Figure 1. We will also compare antibody levels from serum collected by venipuncture versus self-collected using a TASSO device and from fluid collected by nasal swabs. Based on preliminary and published data, we expect a high concordance between antibody levels from capillary blood collected by TASSO and venous blood collected by venipuncture or from a central venous catheter. If there is a slight discrepancy, we can calculate a correction factor based on the results from the paired specimens collected on week 12. If there is an unexpected significant discrepancy between antibody levels that cannot be corrected, we will have a venous blood draw at week 24 to calculate half-life using just venous blood samples. We will monitor for breakthrough SARS-CoV-2 infection by PCR of fluid collected by nasal swabs. If breakthrough infection does occur, we may sequence the spike gene (or entire viral genome) to determine the variant and identify possible resistance mutations. We will also measure anti-drug antibodies in case this is correlated with half-life. We will also monitor routine safety labs as part of standard post-transplant care. Comparisons will be tested using a t-test. As part of an exploratory analysis, we may also calculate the half-life of VIR-7831 and of SARS-CoV-2 neutralizing antibodies in nasal swabs and of SARS-CoV-2 neutralizing antibodies in serum after infusion of VIR-7831.

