## 12.3 Sample Size and Accrual

At the Fred Hutch, we perform approximately 250 allogeneic transplants per year, approximately 5% of which involve umbilical cord blood donors. We also perform approximately 180 autologous transplants per year. The target enrollment for this trial is approximately 50 HCT candidates, of which ten participants will be autologous HCT candidates and 40 will be allogeneic HCT candidates (including cord blood HCT candidates). At least 8 of the allogeneic HCT candidates will be from HLA-mismatched (related or unrelated) HCT recipients. Based on the estimated number of treated patients per year (and previously treated patients since 2013), as well as the estimated number of patients that we may enroll (i.e., ‘feasible’ patients) after accounting for estimated eligibility and consent rates, it will be feasible to enroll approximately 55 subjects over 6-12 months. Our final estimated sample size will be 50 subjects after accounting for an estimated 10% dropout prior to completion of the full 24-week study period. If the dropout rate is higher at three months after mAb infusion, we may enroll more patients to achieve a target of 50 overall subjects. The study is open to anyone regardless of gender or ethnicity. Efforts will be made to extend the accrual to a representative population. If accrual is slow, we may add another site. If accrual of the HLA-mismatched strata is slow, we may analyze and report the results in the HLA-matched strata once that is fully enrolled given the urgency of the pandemic.

- Primary objective: Our primary endpoint is to calculate the half-life of VIR-7831 post-transplant. Based on the half-life seen with other antibodies containing the LS mutation in adults who have not undergone transplant, we anticipate a half-life of up to 3 months. However, this half-life may be shortened in transplant recipients. Since we will use descriptive statistics, the sample size is

sufficient to provide data to calculate the half-life. Levels of VIR-7831 can be measured using an idiotypic antibody assay that is not affected by COVID-19 infection or vaccination.

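### The one-phase half-life planned for serum neutralizing titers mixes infused VIR-7831 with other antibody in participants who are seropositive, vaccinated, infected or (by assumption) given IVIG; the VIR-7831 half-life itself is unaffected.

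*Combined protocol and SAP*

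**What the plan says.** Section 12.1.1, under the primary objective, applies one model to two quantities: "The half-life of the anti-SARS-CoV-2 monoclonal antibody and neutralizing antibody titers in the serum will be calculated by a one-phase exponential decay model". It adds that fold-changes will be normalized to each subject's pre-transplant level.

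The two quantities come from different assays. For the drug level, Sections 12.1.1 and 12.3 rely on specificity: "Levels of VIR-7831 can be measured using an idiotypic antibody assay that is not affected by COVID-19 infection or vaccination". For the titer, Section 9.2 describes a pseudovirus ID50 assay: "this is a functional test to assess the ability of antibodies to bind and prevent infection of cultured cells with a pseudotyped virus". Nothing in that description separates VIR-7831 from other spike-neutralizing antibody.

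The eligibility criteria in Section 5.1 admit other sources of antibody. Prior COVID-19 and prior vaccination are allowed, "or seropositivity for SARS-CoV-2 are permitted", "Post-enrollment vaccination is anticipated and permitted", and "Administration of IVIG before or during the study is permitted". On timing, Section 2 says: "Current guidelines recommend considering vaccination at least three months" after transplant. Section 12.3 says breakthrough infection may be seen, particularly late in the study.

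The status of the titer analysis is not consistent. Section 12.1.1 says the titer half-life will be calculated. The synopsis and Section 3.2 (item 6) list serum neutralization as exploratory, Section 9.2 says the assay may be performed as an exploratory analysis, and Section 12.2 says that half-life may be calculated "of SARS-CoV-2 neutralizing antibodies in serum after infusion of VIR-7831", again as exploratory.

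**The concern.** A mono-exponential fit describes one dose that only declines. It suits VIR-7831 measured by a drug-specific assay. It does not suit a total that other antibody can join. Vaccination three months or more after transplant can fall before the week 16, 20 and 24 samples, and these have the most leverage on the fitted slope. Antibody already present at infusion also enters the curve, with its own rate of loss.

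The plan sees this problem for the drug level and answers it with the choice of assay. It gives no matching protection for titers. Infection, vaccination and medication histories are abstracted (Section 9.1) and nucleoprotein IgG is measured (Section 9.2), but no analysis rule uses them to censor, restrict or adjust. Normalizing to a baseline divides each curve by a constant, which leaves the log slope, and so the half-life, unchanged.

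At stake is the reading of the titer half-life. If it is reported next to the VIR-7831 half-life as a second measure of the same decay, it can mislead.

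**Working it through.** The plan gives no figure for this analysis to reproduce, so the check is an illustration.

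**Inputs from the documents**
- Sampling days 0, 7, 14, 21, 28, 56, 84, 112, 140 and 168 (Appendix A; the day 1 sample named in footnote C is left out).
- A half-life of up to 3 months is anticipated and may be shorter after transplant (Section 12.3). I use 60 days as the main case, with 30 and 90 days alongside.
- A 21-day half-life for ordinary IgG (Sections 1 and 2), used for a decaying background.

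**Assumptions, not in the documents**
- Non-VIR-7831 neutralizing activity of 1% to 25% of the end-of-infusion VIR-7831 titer.
- A late response that appears in full at day 105. Three months is about 91 days after transplant, and infusion precedes conditioning by 1–7 days, so this is close to the earliest guideline-compatible date. The first sample it affects is day 112.
- No measurement noise.

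**Formulas.** VIR-7831 contribution: m(t) = 2^(−t/h). Observed titer: y(t) = m(t) + added antibody. Log-linear fit: slope b of ln y on t, half-life = ln 2 / (−b). Untransformed fit: least squares of y on a·exp(−kt), half-life = ln 2 / k. Section 12.1.1 does not say which scale is meant, so both are shown.

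**One case in full** (h = 60, step of 10% from day 105)
- Late values without the step: 0.274, 0.198, 0.144 at days 112, 140, 168. With it: 0.374, 0.298, 0.244.
- Mean day = 630/10 = 63; sum of squared deviations of day = 32,340; sum of cross-products with ln y = −271.45.
- b = −271.45/32,340 = −0.008394 per day; half-life = 0.6931/0.008394 = 82.6, or 83 days.

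**True half-life 60 days**

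| Added antibody | Log-linear fit | Untransformed fit |
|---|---|---|
| None | 60 | 60 |
| Step 1% from day 105 | 62 | 61 |
| Step 10% | 83 | 74 |
| Step 25% | 129 | 107 |
| Constant background 5% | 68 | 66 |
| Constant background 10% | 76 | 73 |
| 10% background, 21-day half-life | 57 | 56 |

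**Other true half-lives.** With steps of 10% and 25%, a true 30 days fits as 53 and 89 (log-linear) or 35 and 50 (untransformed); a true 90 days fits as 120 and 194 or 113 and 174. A 25% background with a 21-day half-life makes a true 90 days fit as 77 (log-linear).

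**Check of possible remedies**
- Dropping samples after the event (fit to day 84) returns the true value in the step cases: 60 gives 60.
- Subtracting the day-0 titer does harm if the background decays. With a 10% background at a 21-day half-life, the subtracted values at days 112, 140 and 168 are 0.177, 0.099 and 0.044. The log-linear fit gives 39 days for a true 60. For a true 30 days it gives 20, with three late values negative and unusable.
- A free plateau corrects a constant background but not a late rise. With a 10% rise from day 112, a true 90 days fits as 57 (untransformed).

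**The case against.** The strongest reply is that little depends on this figure. The primary endpoint is the half-life of VIR-7831 (Section 12.3), and secondary objective 1 compares the half-life of VIR-7831 between groups (Section 3.2). Both rest on the specific assay. Serum neutralization is called exploratory in four places, and in two of them it is optional. The phrase "of SARS-CoV-2 neutralizing antibodies in serum after infusion of VIR-7831" can also be read as total activity, which need not track the drug. All of this stands and limits the point. A reader might infer that the primary result, or the search for faster decay after mismatched transplant or GVHD, is compromised. The documents do not support that.

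A reader might also infer that the titer half-life is always biased long. It is not: a pre-existing titer that falls faster than VIR-7831 shortens it, and Section 2 expects recipients to lose prior immunity in the first months after transplant.

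The size can be questioned too. The added-titer levels are assumptions, Section 2 expects vaccine responses to be sub-optimal, and at 1% the error is only 1–2 days for a true 60 days. The documents do not say that IVIG contains SARS-CoV-2 neutralizing antibody. These limits are accepted.

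What remains is that Section 12.1.1 places this calculation under the primary objective, says it will be done, names the model, and gives no rule for exposures that the protocol itself permits or anticipates.

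**Conclusion.** The point holds, confined to the neutralizing-titer half-life. In participants with prior seropositivity, vaccination or infection during follow-up, or IVIG if it carries neutralizing antibody, the fitted value mixes infused and other antibody and cannot be relied on as a measure of VIR-7831 decay. It would be too strong to say that it never measures that decay: in a participant with none of these exposures, the titer could track the drug.

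Late added antibody lengthens the estimate. A pre-existing titer can lengthen or shorten it, depending on how fast that titer falls. For a true 60 days the illustration runs from 57 days (10% background decaying at 21 days) to 129 days (25% late step), both log-linear. The error is negligible at a 1% contribution. These sizes rest on the assumed contributions, the day-105 onset and noise-free curves.

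Separately, Section 12.1.1 conflicts with the synopsis and Sections 3.2, 9.2 and 12.2 on whether the titer half-life is exploratory, and these should be reconciled.

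**What to change.** In Sections 12.1.1 and 12.2:

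1. Label the serum titer half-life exploratory, in line with the synopsis and Sections 3.2 and 9.2.
2. Estimate it only from samples taken before the first post-infusion SARS-CoV-2 vaccine dose or PCR-positive infection, and before the first post-infusion IVIG dose, stating the assumption that IVIG may contain neutralizing antibody.
3. Restrict it to subjects with a negative pre-infusion titer, because censoring alone does not remove antibody already present.
4. State whether the fit is log-linear or untransformed.
5. Present all other titers descriptively as total neutralizing activity.
6. Base statements about monoclonal antibody decay on the VIR-7831 assay only.

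Do not subtract the day-0 titer: if that background decays, subtraction creates falsely fast decay.

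The pre-infusion sample and the vaccination, infection and medication histories are already scheduled, so the change needs only analysis wording and a censoring flag. The cost is fewer subjects and fewer late points, so a wider interval for the titer half-life. The documents do not say how many subjects will have a negative pre-infusion titer; if there are few, the titers may have to be reported descriptively only. The VIR-7831 half-life analysis does not change.
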